## 6. Drugs/ Substances/ Devices

TheraSphere® consists of insoluble glass microspheres where Y is an integral constituent of the glass. The mean sphere diameter ranges from 20 to 30  $\mu$ m. Each milligram contains between 22,000 and 73,000 microspheres. TheraSphere® is supplied in 0.6 mL of sterile, pyrogen-free water contained in a 1.0 mL vee-bottom vial secured within a 12 mm clear acrylic vial shield. TheraSphere® is available in six activity sizes: 3 GBq (81 mCi), 5 GBq (135 mCi), 7 GBq (189 mCi), 10 GBq (270 mCi), 15 GBq (405 mCi) and 20 GBq (540 mCi). TheraSphere® is also available in custom dose sizes in increments of 0.5 GBq between 3 GBq and 20 GBq.

TheraSphere® is delivered into the liver tumor through a catheter placed into the hepatic artery. The hepatic artery provides the main blood supply to the tumor in the liver, whereas the portal vein supplies blood to normal liver parenchyma. TheraSphere® is embolized within the tumor and exerts a local beta radiation radiotherapeutic effect with relatively limited concurrent injury to surrounding normal tissue.

Hepatic resection of liver metastases is currently the only potentially curative therapy. Unfortunately, curative resection is possible in less than 20% of those patients with metastases to the liver [4]. Over the past two decades, more frequent screening and the introduction of new anticancer agents has resulted in decreases in the incidence and mortality associated with colorectal cancer, *inter alia*. According to SEER data, the annualized percent change in incidence decreased 2.5% between 1998 and 2008 while the annualized percent change in mortality was negative in every period analyzed between 1978 and 2007.

As an example of secondary malignancy, systemic therapies for CRC include cytotoxic agents (fluoropyrimidines, irinotecan, oxaliplatin) and targeted therapies that inhibit tumor growth (vascular endothelial growth factor and epidermal growth factor targeting agents). The identification of the KRAS biomarker has further refined therapeutic options. Patients with CRC who fail first-line chemotherapy, typically an oxaliplatin based therapies have a poor prognosis. According to a recent study by Peeters et al, patients treated with second-line FOLFIRI have a median PFS of 3.9 months (wild-type KRAS) to 4.9 months (mutant type KRAS). Adding panitumumab was shown to improve median PFS to 5.9 months in wild-type KRAS patients and had no impact on PFS (median 5.0 months) in mutant-type KRAS patients [12].

While CRC metastatic to the liver is considered Stage IV disease, advances in perioperative care, imaging and surgical techniques have supported development of liver-directed therapies which may be used alone, in combination with chemotherapy, or integrated with surgical approaches.

Liver directed radiotherapy using external beam radiotherapy to the liver is limited by the higher sensitivity to radiation of normal liver parenchyma versus tumor and the subsequent risk of radiation induced liver disease. Localized delivery of radiation through radioembolization using Y microspheres has shown encouraging results as a well-tolerated treatment with good response rates in an increasing body of literature [13].

## 7. Study Statistics

We propose to combine the studies acquired here with those from a previous study that included data from 17 patients. Statistical Considerations. The goal is to test whether the pre-therapy estimate of liver dose is within 10% of that of the post-therapy estimates. Based on simulation and phantom experiments, we assume that the standard deviation for Y estimates of liver dose is 5%. A sample size of 20 will have 95% power to detect such a difference at a significance level of 0.05.

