Most importantly from the standpoint of being able to predict normal organ dose and therefore provide safe and effective treatment planning, we also compared the tumor and treated normal liver doses estimated from MAA SPECT with those from post-therapy  $^{90}\text{Y}$  QBSPECT. The differences in the liver AD ranged from -8 to 6% (mean  $1\% \pm 6\%$ ), indicating that the MAA can predict normal liver AD very accurately, even in extreme cases where the correlation is not visually apparent. Moreover, as is consistent with experience from a wide range of experience in all RPTs (refs), the average absorbed dose to the dose limiting normal organ (liver) varied widely from patient to patient indicating the potential for a significant safe increase in potential activity administered (average of 60 %) and consequently a proportionately higher absorbed dose to the tumor and a probable increase in the chance of tumor control (calculated as 99.8 % of tumor control probability vs. 72 % using the tumor control threshold of 235 Gy as established by Garin et al. [8]).

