#### 4. Study Procedures

This is an observational treatment use protocol that will provide IRB oversight and documentation of the clinical experience of patients undergoing treatment for metastatic colorectal cancer in the liver using TheraSphere® under an HDE, IRB00078140 / CR00021884. We proposed to enroll 3-5 patients from this clinical treatment group. Study participation involves an additional post-treatment SPECT/CT or PET/CT scan (up to 12 hours post-treatment). Patients will be followed for treatment-related adverse experiences for a minimum of 30 days after each treatment per clinical protocol.

Patients shall be screened to be enrolled and, if eligible, the physician and patient will discuss a standard of care TheraSphere® treatment plan. The patient will be asked to provide consent in accordance with IRB approval.

Prior to initial treatment, standard of care Shunt Study, the  $^{99\text{m}}\text{Tc}$  MAA SPECT/CT scan of the liver and lungs will be performed using standard institutional practices.

The TheraSphere® dose will be ordered (per standard of care) and initial treatment scheduled. TheraSphere® treatment will be performed in an outpatient setting.

Following treatment, patients will remain at the hospital under medical observation until the physician determines that they can safely be discharged to home. The patient will undergo an additional SPECT/CT or PET/CT scan of the liver and lungs which is not part of the standard of care at up to 12 hours post-treatment. All patients will be evaluated 3-6 weeks post-treatment to assess clinical experience and adverse experiences. Subsequently, patient status will be followed via communication with the referring physician to determine disease status and long term treatment outcome according to standard of care practice.

Patients will have 1-2 outpatient visits for pre-treatment evaluation to determine initial eligibility to receive TheraSphere®, followed by a treatment visit for outpatient delivery of TheraSphere®, and at least 1 follow-up visit 3-6 weeks after initial treatment.

If more than one treatment is given, additional follow-up visits will occur after each treatment following institutional guidelines. Subsequent follow-up contacts will be made with the referring physician. Patients will be asked to provide consent for medical record review after treatment.

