## Data Analysis

We propose to use the data obtained from the 3 patients participating in this study along with data from 17 patients available from a previous IRB-approved study to assess the ability of 99mTc MAA SPECT/CT images to predict Y dose to the liver estimated from post-Therapy Y imaging. To do this, the MAA and Y images will be reconstructed and quantified to obtain 3D activity distribution images. Tumors and normal liver regions will be delineated with the aid of CBCT and diagnostic CT or MRI images. We will use the average activities in the tumors and normal liver parenchyma obtained in the MAA images to estimate the Y activity that would be delivered to each region. We will then apply 3D dosimetry methods [10, 11] to calculate the average doses to the tumors and normal liver parenchyma from both the Y images and the

estimated Y distribution obtained from the SPECT/CT images. We will then compare the dose estimates to these to tumors and normal liver obtained by these two methods.

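### Section 7 sets an agreement goal (within 10%) but sizes the study in the wording of a difference test, and no agreement hypothesis or criterion is stated anywhere

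*Combined protocol and SAP*

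**What the plan says.** Section 7 (Study Statistics) gives the aim as "The goal is to test whether the pre-therapy estimate of liver dose is within 10% of that of the post-therapy estimates". It assumes a 5% standard deviation for the ⁹⁰Y estimate of liver dose and then says "A sample size of 20 will have 95% power to detect such a difference at a significance level of 0.05". It does not say whether the test is one- or two-sided.

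The Data Analysis part of Section 4 explains where the 20 come from: "data obtained from the 3 patients participating in this study along with data from 17 patients". Elsewhere Section 4 allows slightly more: "We proposed to enroll 3-5 patients from this clinical treatment group", which would make 20 to 22 in all. On method, Data Analysis says only that the dose estimates from the two imaging routes will be compared, for tumour and for normal liver. No section gives a null and alternative hypothesis, a named test, a confidence-interval rule or limits of agreement.

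Section 3 (Background) reports earlier paired results in patients with hepatocellular carcinoma: "The differences in the liver AD ranged from -8 to 6" percent, with a mean of 1% ± 6%.

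**The concern.** The two statements in Section 7 point in opposite directions. To show that two doses agree within 10%, the null hypothesis must be that they differ by 10% or more, and rejecting it supports agreement. A test with power to detect a difference has a null of no difference, and rejecting it supports disagreement.

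This matters because the comparison is the study's only stated objective and Section 7 is the only place where its inference is described. An analyst who followed the power sentence literally would report a significant difference for a small, precisely measured bias that the 10% goal treats as acceptable.

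**Working it through.** **Inputs**

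- Margin ±10%, α = 0.05, N = 20, stated power 95%: Section 7.
- SD 5%: Section 7, where it is given for the ⁹⁰Y dose estimate. Using it as the SD of the paired MAA-minus-⁹⁰Y difference is an assumption. If both estimates had independent errors of 5%, the SD of the difference would be 5% × √2 = 7.07%.
- Earlier paired differences, mean 1% ± 6%: Section 3, with the ± assumed to be an SD.

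**Step 1. The plan's own figure.** A paired t-test against zero, N = 20, true difference 10%, has power above 99.9% at an SD of 5% or 7.07%, one- or two-sided. Read as two independent groups of 10 (SD 5%), the power is 98.8%. The stated 95% is not reproduced by these readings. A paired two-sided test does give 95% if the true difference is 4.3% at SD 5%, or if the SD of the difference is about 11.8% at a true difference of 10%. So the stated figure does not identify which test was meant.

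**Step 2. Where the two rules part company (N = 20, sample SD 5%).**

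- Standard error = 5/√20 = 1.118%.
- Difference test, two-sided 0.05: significant when |mean| > t(0.975, 19) × SE = 2.093 × 1.118 = 2.34%.
- Equivalence rule, two one-sided tests at 0.05: the half-width of the 90% confidence interval is t(0.95, 19) × SE = 1.729 × 1.118 = 1.93%, so it passes when |mean| < 10 − 1.93 = 8.07%.

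An observed mean difference between 2.34% and 8.07% in size is therefore both significantly different from zero and inside the margin.

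**Step 3. How often this happens.** The first result column uses the non-central t distribution with non-centrality bias × √20/SD. The second uses simulated trials.

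| True bias | SD | Test against zero is significant | 90% CI inside ±10% |
|---|---|---|---|
| 1% | 5% | 14% | >99.9% |
| 1% | 6% | 11% | >99.9% |
| 3% | 5% | 72% | >99.9% |
| 4% | 5% | 92% | >99.9% |
| 5% | 5% | 98.9% | 99.6% |

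**Step 4. The opposite error.** Probability that the test against zero is non-significant when the true bias is 10%:

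| SD of paired difference | Non-significant |
|---|---|
| 5% to 7.07% | 0.003% or less |
| 10% | 1.1% |
| 20% (assumed) | 44% |

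**Step 5. Is N = 20 enough for an equivalence test of the mean?** Power is above 99.9% for a true bias of 0 to 1% and an SD of 5% to 6%. At a true bias of 5% it is 99.6% (SD 5%), 97.5% (SD 6%) and 92.1% (SD 7.07%).

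**Step 6. Mean or individual agreement?** With mean 1%, SD 6% and normal differences, the share of patients within ±10% is Φ(9/6) − Φ(−11/6) = 90%. The estimated 95% limits of agreement (mean ± 1.96 SD) would lie inside ±10% in about 8% of trials of 20 patients, or about 38% with zero bias and SD 5%. Agreement of the mean and agreement in each patient are therefore separate claims.

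**The case against.** The strongest defence is that the plan states no decision rule. The goal sentence runs in the agreement direction, and the power sentence may be loose shorthand for an equivalence test or for the ability to notice a departure as large as 10%. That stands. A reader might infer that the sponsor will treat a significant result as failure and a non-significant one as proof of agreement; the documents say neither. The defence does not remove the gap, because on the lenient reading the equivalence hypotheses are still missing and the same correction is needed.

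A reader might also infer that noisy data with a bias at the margin could easily pass as agreement. The documents' own figures do not support this: the 44% in Step 4 needs an SD four times the planned 5% and more than three times the earlier 6%.

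It is also fair to say that at the earlier mean difference of 1% the conflict is modest, at 11% to 14% of trials. That mean comes from hepatocellular carcinoma, whereas this study enrols secondary malignancies, so a larger bias cannot be ruled out; nothing in the documents predicts one either.

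Finally, this is a feasibility study with 3-5 new patients, and Section 4 says the extra scan does not affect therapy. That lowers the urgency. It does not make the only inferential statement right.

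**Conclusion.** The power sentence is wrong as written for the stated goal, and no agreement criterion exists to correct it. Applied literally, it would flag observed mean differences above 2.34%, under a quarter of the margin. The resulting conflict with the goal ranges from 11-14% of trials at a 1% bias to 98.9% at a 5% bias.

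These figures assume a two-sided paired t-test, N = 20, normally distributed percentage differences, and an SD of the paired difference of 5% (6% where stated). They describe what follows if the sentence is taken at its word, not a rule the plan has adopted. The fault lies in the hypothesis and not in the sample size. Severity: should be fixed, before the doses are compared.

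**What to change.** Replace the power sentence in Section 7 with wording to this effect:

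- For each patient, take the percentage difference (MAA dose minus ⁹⁰Y dose)/⁹⁰Y dose for liver. The null hypothesis is that the absolute mean percentage difference is 10% or more; the alternative is that it is below 10%.
- Agreement of the mean is concluded only if the two-sided 90% confidence interval lies wholly between −10% and +10% (two one-sided tests, each at 0.05). A p-value against zero difference will not be used to conclude agreement or disagreement.
- The criterion concerns the mean. The 95% limits of agreement will be reported beside it to describe agreement in individual patients.
- Restate the power for this test: above 99.9% with 20 patients, a true bias of 0 to 1% and an SD of the paired difference of 5% to 6%. Say why that SD is appropriate for the paired difference.

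If the sponsor intends the 10% to apply to each patient, Section 7 should say so, because a test of the mean does not answer that question.

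The cost is two or three sentences and a little extra reporting, with no added patients or scans.

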## 8. Risks

The medical risk of our study includes an additional SPECT/CT or PET/CT post-administration as well as a SPECT/CT of the pre-therapeutic 99mTc-MAA. The estimated equivalent dose to the patient from these two scans is on the order of 10-20 mSv or 10-20 mGy. While this may in theory represent an increased stochastic risk of cancer induction, the value must be taken in comparison with the 120 Gy of absorbed dose from the therapy itself, a value ~ 10000 times higher than the absorbed dose from the diagnostic 3D imaging scans; in fact the dose from the scans represent about 0.1 % of the potential error or variability in the dose allowed in the treatment.

Minimization of this risk includes only obtaining one field of view per time point. Also, a low-dose CT scan appropriate for attenuation correction will be performed as part of the of SPECT/CT or PET/CT scans in order to reduce X-ray exposure.

Legal risks include the existence of a patient key on the secure department drive that is encrypted. This list is necessary for recovering clinical data elements needed for study follow-up. After the study, all documents with the patient's name will be destroyed except for the initial consent which will be maintained in a locked cabinet. The consent will be destroyed within one year of death of patient or after 3 years if lost to follow up. There are no financial risks to the participants.

## **9. Data Safety and Monitoring**

The SKCCC Compliance Monitoring Program will provide external monitoring for JHU-affiliated sites in accordance with SKCCC DSMP (Version 6.0, 02/21/2019). The SMC Subcommittee will determine the level of patient safety risk and level/frequency of monitoring.

## **10. Benefits**

Results from this study could benefit society as they could be used to identify the patients with liver neoplasia who many benefit from personalized dosimetry-based treatment planning for TARE and therefore increased activity and dose to the disease site.

## **11. Payment and Remuneration**

The participants will not be compensated for participation in this study.

## **12. Costs**

The cost for the additional post-implant PET/CT or SPECT/CT scan will be paid for by the investigators. No additional costs will be incurred by the patient for the research component.

